### **4.4 Pharmacokinetic Population**

The PK population is a subset of the randomized population and consists of all randomized subjects for whom at least one nicotine PK parameter can be derived. This population will also be applied for the PD parameters. Only subjects without major protocol deviations (see [Section 4.4.1](#)) which have an impact on evaluability of the main objective will be included in the PK population.

#### **4.4.1 Protocol Deviations**

Protocol deviations are considered as deviations from the study procedures as defined in the study protocol, including but not limited to, as any violation of inclusion/exclusion criteria, mis-randomizations, assessments not performed or performed outside the scheduled time

Philip Morris Products S.A.  
 THS Induction device and regular or menthol sticks, P1-PK-12  
 [REDACTED] CA39924

---

windows, or use of drugs that are known to affect components of the “smokers’ health profile.”

Major protocol deviations are a subset of protocol deviations that may significantly impact the completeness, accuracy, and/or reliability of the study data or that may significantly affect a subject's rights, safety, or well-being.

Subjects with major protocol deviations will be identified to determine whether they will be excluded from any of the analysis populations.

Major deviations will include but are not limited to the deviations presented in Table 4.1.

**Table 4.1 Definition of Major Protocol Deviations Categories**

Sub-Category	Description
Protocol violation	Violation of inclusion/exclusion criteria. Or missing documentation of any of the inclusion/exclusion criteria at time of enrollment.
Procedural deviation	Deviation to any study procedures.
Mis-randomization	Misclassification of subject's sex at randomization. Or incorrect product administered according to randomized sequence.
Use of TNP not allowed	Use of any nicotine or tobacco-containing product other than the assigned product during the exposure period, or use of any nicotine tobacco-containing product during at least 23 hours of abstinence from any nicotine/tobacco containing products (nicotine wash-out).

## 5. PRODUCT DESCRIPTIONS

### 5.1 Test Products

Test product will be the THS induction device with regular and menthol sticks, provided by the Sponsor. The following two stick variants will be investigated:

Name in the study (sticks)	Flavor
P1R stick	Regular
P1M stick	Menthol

The test products will be listed as:

Name in the study (test products)	Abbreviated name (test products)
THS regular stick (P1R)	P1R
THS menthol stick (P1M)	P1M

Philip Morris Products S.A.  
 THS Induction device and regular or menthol sticks, P1-PK-12  
 [REDACTED] CA39924

---

## 5.2 Comparator Product

The subjects will bring their own supply of commercially available single brand CIG for the study duration.

The comparator product will be listed as:

Name in the study (comparator product)	Abbreviated name (comparator product)
Combustible cigarette	CIG

All subjects eligible at Screening visit and invited for Baseline visit Day -1 will be asked to purchase their usual brand of CIG and to provide it to the site personnel at their admission on Baseline (Day -1). Every subject will bring an unopened pack of CIG which will be kept in secured storage room at site with access limited to authorized personnel.

## 6. PHARMACOKINETIC ANALYSIS

### 6.1 Collection Schedule for Plasma Nicotine

Collection schedule is described in [Table 6.1](#).

**Table 6.1 Plasma Nicotine Samples Collection Schedule**

Day 1 (14 blood samples)	Prior to the start of product use (TB0) $\leq$ 5 min ( $\pm$ 2 min) prior to T0.  In relation to T0 from Day 1: TB1 after 4 minute $\pm$ 30 seconds, TB2 after 6 minutes $\pm$ 1 minute, TB3 after 8 minutes $\pm$ 1 minute, TB4 after 10 minutes $\pm$ 1 minute, TB5 after 12 minutes $\pm$ 1 minute, TB6 after 15 minutes $\pm$ 2 minutes, TB7 after 30 minutes $\pm$ 5 minutes, TB8 after 1 hour $\pm$ 5 minutes, TB9 after 2 hours $\pm$ 5 minutes, TB10 after 4 hours $\pm$ 5 minute, TB11 after 10 hours $\pm$ 5 minutes, TB12 after 14 hours $\pm$ 5 minutes, TB13 after 24 hours $\pm$ 10 minutes
Day 2 (13 blood samples)	Same time points from TB1 to TB13. TB0 for Day 2 will be the same sample taken as TB13 on Day 1.
Day 3 (11 blood samples)	Same time points from TB1 to TB11 and no samples for TB12, TB13. TB0 for Day 3 will be the same sample taken as TB13 on Day 2.

### 6.2 Plasma Nicotine Concentrations

Analytical Laboratory

Samples will be analyzed for nicotine in plasma using a validated liquid chromatography coupled to tandem mass spectrometry (LC-MS/MS) detection analytical method with the appropriate quality controls in accordance with the Food and Drug Administration (FDA)

Philip Morris Products S.A.  
 THS Induction device and regular or menthol sticks, P1-PK-12  
 [REDACTED] CA39924

---

Guidance for Industry: Bioanalytical Method Validation (May, 2001) and in accordance with FDA Good Laboratory Practice regulations (Title 21 CFR Part 58) at [REDACTED] Bioanalytical Services Lincoln, Nebraska.

### 6.3 Plasma Nicotine Pharmacokinetic Parameters

Nicotine PK endpoints will be derived from measured plasma nicotine concentration-time data. Nicotine PK parameters will be derived using a non-compartmental analysis (NCA) technique using appropriate and validated PK software (e.g., Phoenix WinNonlin version 8.3.4 or higher).

For values above the upper limit of quantification (ULOQ), the ULOQ will be used for calculation and reporting in summary tables. For nicotine concentrations below the LLOQ (BLQ) for the calculation of descriptive statistics of observed plasma nicotine concentrations: In general, BLQ values before T0 will be imputed by LLOQ/2.

Plasma concentrations as determined at the collection times described in [Section 6.1](#) will be used for the calculation of the plasma nicotine PK parameters.

BLQ values after the last quantifiable value are not included in the analysis (e.g., for the calculation of AUC).

Any BLQ value (after T0 and before the last quantifiable value) would need to be queried\* and, if confirmed, it will be imputed by LLOQ/2.

\*The query will be triggered at the latest by [REDACTED] data QC, and [REDACTED] will query the bioanalytical laboratory. The information on the value queried and a summarized response from the bioanalytical laboratory will be part of the SDTM data (e.g. in the CO domain).

The number and percent of values below LLOQ or above ULOQ will be presented in each summary table. If 50% or more data are below LLOQ or above ULOQ, only the number and percent of values below LLOQ or above ULOQ will be reported in the summaries, together with minimum (= LLOQ/2) and maximum (= ULOQ) of the observed values.

In particular, the following PK parameters will be derived from measured nicotine concentration-time data following IP use:

Cmax	Maximum nicotine plasma concentration. Cmax will be reported as long as there is at least one quantifiable concentration post T0.
Tmax	Time to maximum nicotine plasma concentration Cmax.
AUC0-24	Area under the curve of nicotine plasma concentration-time computed from T0 to T=24 hours [AUC0-24h].
AUC0-Tmax	Area under the curve of nicotine plasma concentration-time computed from T0 to the subject-specific time of maximum nicotine concentration [AUC0-Tmax].

All AUC parameters will be calculated using linear trapezoidal with linear interpolation method.

Philip Morris Products S.A.  
 THS Induction device and regular or menthol sticks, P1-PK-12  
 [REDACTED] CA39924

---

For PK analyses, baseline (pre-product use concentration) will be defined as the last assessment prior to T0 (5 minutes prior to T0) for each study day of exposure. PK parameters will not be calculated for subjects with less than 3 consecutive post-product use time points with quantifiable concentrations. Subjects for whom there are insufficient data to calculate the PK parameters will be included in the concentration tables and individual concentration-time figures only and excluded from the summary and statistical analysis.

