12.1.2 Definitions for Statistical Data Analysis

For PK and PD analyses, baseline will be defined as the last assessment prior to T0 (5 minutes prior to T0 for blood sampling and 15 minutes for VAS questionnaires) for each study day of exposure.

Nicotine PK parameters (T_{max} , C_{max} , AUC_{0-24h} and AUC_{0-t}) will be derived from measured plasma nicotine concentrations-time data. Nicotine PK parameters will be derived from plasma nicotine concentration versus time data using a non-compartmental analysis (NCA) technique. All PK parameters will be computed in measured plasma nicotine concentration-time. Indeed, due to the study requirement of at minimum 23 hours of nicotine abstinence before any IP use and the typical half-life of plasma nicotine of about 2 hours [23]. Then after 23 hours of nicotine abstinence it is expected that a maximum of 0.05% of nicotine will be present. Descriptive Statistics

All data will be presented in listings, ordered by subject, study visit, IP, and time point, unless otherwise specified.

For continuous data, summary statistics will include the number of subjects (n), the number and percent of subjects with missing data, the arithmetic mean, arithmetic standard deviation (SD), 95% confidence interval (CI) of the arithmetic mean, median, first and third quartiles, minimum, maximum; for log-normal data, the geometric mean, geometric coefficient of variation (CV), and 95% CI of the geometric mean will be presented instead of arithmetic mean, SD, and 95% CI of the arithmetic mean, respectively.

For log normally distributed endpoints (C_{max} , AUC_{0-24h} and AUC_{0-t}), geometric mean, geometric CV, and confidence interval will be presented additionally.

Confidentiality Statement

Data and information contained in this document are considered to constitute trade secrets and confidential commercial information, and the legal protections provided to such trade secrets and confidential information are hereby claimed under the provisions of applicable law. No part of this document may be publicly disclosed without the written consent of Philip Morris Products S.A.

Nominal categorical variables will be summarized by frequency statistics (number and percentage), including the number of missing data as a category.

Ordinal categorical data (e.g., T_{max}) will be summarized by number of subjects (n), number and percent of subjects with missing data, median, first and third quartiles, and minimum and maximum.

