12.1.3 Handling of Missing Values and of Values outside the Detection Limits

In general, missing data will not be imputed in this study, due to the nature of the measurements and the short periods of exposure and use. However, for questionnaire data, total scores and domain or subscale scores may use a certain degree of imputation by averaging across individual item scores. Further details will be provided in the SAP.

In general, bioanalytical values below the lower limit of quantification (LLOQ) will be imputed using $0.5 \times$ lower limit of quantification. For values above the upper limit of quantification (ULOQ), the ULOQ will be used for calculation and reporting in summary tables.

For nicotine concentrations below the LLOQ (BLOQ):

- BLOQ values before T_0 will be imputed by LLOQ/2
- BLOQ values after the last quantifiable value are not included in the analysis (e.g., for the calculation of AUC)
- Any BLOQ value (after T_0 and before the last quantifiable value) would need to be queried and, if confirmed, it will be imputed by LLOQ/2.

The number and percent of values below LLOQ or above ULOQ will be presented in each summary table.

Confidentiality Statement

Data and information contained in this document are considered to constitute trade secrets and confidential commercial information, and the legal protections provided to such trade secrets and confidential information are hereby claimed under the provisions of applicable law. No part of this document may be publicly disclosed without the written consent of Philip Morris Products S.A.

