**Note: Plasma Nicotine Concentration Tables (CPCONC1) will have the following format:**

Page 1 of X

Table Plasma Nicotine Concentrations (ng/mL) Following THS Regular stick (P1R) (PK Population)

Subject Number	Product Sequence	Sex	Sample Times (minutes)											
			Pre-use	XX										
XX	XXXXXX	X	XX	XX	XX	XX	XX	XX	XX	XX	XX	XX	XX	XX
XX	XXXXXX	X	XX	XX	XX	XX	XX	XX	XX	XX	XX	XX	XX	XX
XX	XXXXXX	X	XX	XX	XX	XX	XX	XX	XX	XX	XX	XX	XX	XX
n		X		X	X	X	X	X	X	X	X	X	X	X
n missing		X		X	X	X	X	X	X	X	X	X	X	X
% n missing		X		X	X	X	X	X	X	X	X	X	X	X
Mean		X.X		X.X										
SD		X.XX		X.XX										
95% CI		X.X-X,X		X.X-X,X										
Minimum		XX		XX										
1st quartile		X.X		X.X										
Median		X.X		X.X										
3rd quartile		X.X		X.X										
Maximum		XX		XX										

Program: /CAXXXX/sas\_prg/pksas/PROGRAMNAME.SAS DDMMYYYY HH:MM

Programming Notes: For the 95% CI (of Mean), the lower and upper limits may be presented on different rows if the space limit requires it. If there is at least a difference of 1 subject between the Randomized and PK populations, a column for population will be added as the first column and the summary statistics will be presented for each population with table title updated to reflect the populations used in the analysis.

The number and percent of values below LLOQ or above ULOQ are to be presented in each summary table. If 50% or more data are below LLOQ or above ULOQ, only the number and percent of values below LLOQ or above ULOQ is to be reported in the summaries, together with minimum (= LLOQ/2) and maximum (= ULOQ) of the observed values.

Footnotes to include under the table, as appropriate:

<. = Concentration value missing or not reportable.>

<Concentration values that were below the limit of quantitation (BLQ) of 0.200 ng/mL were set to one-half of the limit of quantitation for the calculation of summary statistics.>

Sample Times are listed in Section 6.1. Descriptive statistics precision is specified in Section 6.4.

Philip Morris Products S.A.

THS Induction device and regular or menthol sticks, P1-PK-12

CA39924

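### SAP 6.3 defines AUC0-24h to 24 hours but gives no rule for the area after the last quantifiable sample; followed literally with the linear trapezoid, it biases the THS/CIG ratios by about 2 to 4% and widens their intervals by about 14 to 15%

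*SAP*

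**What the plan says.** SAP 6.3 defines the endpoint as "Area under the curve of nicotine plasma concentration-time computed from T0 to T=24 hours". The same section fixes the integration method: "All AUC parameters will be calculated using linear trapezoidal with linear interpolation method". It also removes late values below the limit: "BLQ values after the last quantifiable value are not included in the analysis (e.g., for the calculation of AUC"). Protocol 12.1.3 has the same exclusion: "BLOQ values after the last quantifiable value are not included in the analysis (e.g., for the calculation of AUC").

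The last samples are at 4, 10, 14 and 24 hours on Days 1 and 2. On Day 3 the last is at 10 hours (Protocol 4.1; SAP Table 6.1). Protocol 12.1.2 gives "typical half-life of plasma nicotine of about 2 hours". The only LLOQ in the documents is in the footnote to the SAP concentration-table shell CPCONC1, for values "below the limit of quantitation (BLQ) of 0.200 ng/mL".

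Neither document mentions a terminal slope, an extrapolation, or any other way to fill the area between the last quantifiable sample and 24 hours.

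**The concern.** The endpoint is named for a window that the stated rules do not reach. If trailing BLQ values are dropped and nothing replaces them, the area stops wherever the concentration last exceeded 0.200 ng/mL. That point depends on the concentration itself, so the lower-delivery product is cut earlier more often. An error of this kind does not cancel in the THS/CIG ratio.

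The samples are also widely spaced where it matters. A single 10-hour value just above or just below the LLOQ decides whether a large, linearly overstated 4-to-10-hour area is counted or lost. That adds noise within subjects. At stake are the geometric mean ratio and interval for AUC0-24h, and the per-product values that the study sets out to describe.

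**Working it through.** **Inputs.** Half-life 2 h (Protocol 12.1.2). LLOQ 0.200 ng/mL (SAP shell CPCONC1). Cmax geometric means 10, 12 and 14 ng/mL for menthol, regular and CIG, with a common GSD of 0.8 (Protocol 12.7.3.1). A geometric SD cannot be below 1, so 0.8 is read as the SD on the log scale. Assumed here: linear rise to a peak at 8 minutes, then a single-phase decline. The protocol refers to a within-subject correlation but gives no value.

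**The plan's own figures.** Protocol 12.1.2 expects at most 0.05% of nicotine after 23 h; 0.5^(23/2) = 0.035%, which agrees. The Cmax precision of 0.191 (Protocol 12.7.3) is reproduced for regular/CIG at a correlation near 0.79 (0.192 at 0.79, 0.190 at 0.795), so about 0.8 is the central case.

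**Where the area stops.** After the peak, C(t) = Cmax × 2^(-(t - 0.133)/2). A sample at t is quantifiable if Cmax ≥ 0.2 × 2^((t - 0.133)/2): 6.1 ng/mL at 10 h, 24.4 at 14 h and 782 at 24 h. The probability is Φ(ln(GeoM/threshold)/0.8). The 14-hour share is multiplied by 2/3, because one period in three is Day 3.

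| Last usable sample | Menthol | Regular | CIG |
|---|---|---|---|
| 4 h or earlier | 26.9% | 20.0% | 15.0% |
| 10 h | 64.3% | 67.6% | 68.8% |
| 14 h | 8.8% | 12.5% | 16.2% |
| 24 h | about 0 | about 0 | about 0 |

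**The 4-to-10-hour gap.** Here C10 = C4/8. Linear: 6 × (C4 + C4/8)/2 = 3.375 × C4. True: (C4 - C4/8) × 2/ln 2 = 2.525 × C4. The linear rule is 34% too high. A 10-hour value of 0.201 implies 1.608 at 4 h and adds 6 × (1.608 + 0.201)/2 = 5.4 ng·h/mL (true 4.1). A value of 0.199 adds nothing. The true total is about 2.95 × 6.14 = 18.1 ng·h/mL.

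**Effect on the ratio.** At the planned sampling times, the linear area divided by the true AUC0-24h is 0.757 if it ends at 4 h, 1.056 at 10 h and 1.084 at 14 h (logs -0.278, 0.055, 0.081). The mean log error per product is:

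- Menthol: 0.269 × (-0.278) + 0.643 × 0.055 + 0.088 × 0.081 = -0.032
- Regular: 0.200 × (-0.278) + 0.676 × 0.055 + 0.125 × 0.081 = -0.008
- CIG: 0.150 × (-0.278) + 0.688 × 0.055 + 0.162 × 0.081 = +0.009

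Menthol minus CIG is about -0.041, a ratio about 4% too low. Regular minus CIG is about -0.017, about 1.7% too low.

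**Effect on the interval.** Trials of 30 subjects in six sequences were simulated 10,000 times at correlation 0.79, with a crossover ANOVA on the log scale. The median 95% CI log-width is 0.431 under the planned rule and 0.377 for the true AUC: 0.431/0.377 = 1.14. Separate paired intervals for menthol give 0.438/0.383 = 1.14. The widening is 13% at correlation 0.5, 15% at 0.8 and 16% at 0.9. The simulated ratios are 0.684 and 0.843, against true values of 10/14 = 0.714 and 12/14 = 0.857.

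**Longer half-life (assumed).** At 2.5 h the menthol bias is about -2% and intervals are about 8% wider. At 3 h it is about -1%, with intervals 4 to 5% wider.

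**If the software extrapolates to 24 h but stays linear between samples.** The missing areas (25.6%, 3.2% and 0.8% of the total after 4, 10 and 14 h) are added back, so the three quotients become 1.013, 1.088 and 1.092. Weighted as above on the log scale, they give +6.8% for menthol and +7.7% for CIG, a menthol/CIG bias of about -0.9%. Simulated width is 0.387/0.377, about 3% extra.

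**With linear-up/log-down and extrapolation.** Ratios return to 0.714 and 0.858, with a width ratio of 1.00.

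**The case against.** The strongest reply is that the SAP never says that the area ends at the last quantifiable sample. It defines the parameter to 24 hours, excludes trailing BLQ values, and leaves the calculation to validated software. Excluding those values is compatible with extrapolating from the last usable one. This stands: a reader might infer that truncation is planned, but the documents support only that no completion rule is written. The headline sizes are therefore conditional on no extrapolation.

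Other stronger readings also fail:

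- A reader might be alarmed that almost no profile is quantifiable at 24 hours. At a 2-hour half-life only about 3% of the area lies beyond 10 hours. The choice between a 4-hour and a 10-hour end does most of the damage.
- A reader might blame the missing Day 3 samples. Collecting them would barely change the width (0.432 against 0.431). They matter because a completion rule must cover them.
- A reader might let half-life vary between subjects. With 20% variation and 8% assay noise, the shares stopping by 4 hours rise to 34%, 28% and 24%. The documents give neither figure.
- The linear trapezoid alone is a common convention. Carried to 24 hours it overstates each AUC by about 10%, which largely cancels in the ratio.

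The consequence is also bounded. The study has no hypothesis, success criterion or significance level, and Cmax and Tmax are untouched. A 4% bias is about one fifth of the interval's half-width on the log scale (0.041 against 0.431/2 = 0.216), and the menthol interval still covers the true ratio in 91 to 93% of simulated trials at correlations 0.9 and 0.8. Reported BLQ counts and individual profiles would show early cut-offs.

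What remains is that a main endpoint depends on an unwritten software setting, and that the linear rule leaves some error under either reading.

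**Conclusion.** The point holds as a gap in the specification of AUC0-24h, with a measurable cost if the written rules are applied as they stand: menthol/CIG about 4% too low, regular/CIG about 1.7% too low, and intervals about 14 to 15% wider. Per-product errors differ in sign, about -3% for menthol and +1% for CIG. These sizes rest on the 2-hour half-life, the 0.200 ng/mL LLOQ, 0.8 read as a log SD, an assumed 8-minute peak, single-phase decline and a correlation near 0.8. The direction held in every half-life examined (1.5 to 3 hours), but the size falls as the half-life lengthens. Unstated extrapolation would remove most of the harm but not all of it. The change should be made before the analysis; the problem does not threaten the study's main description of nicotine delivery.

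**What to change.** In SAP 6.3, compute AUC0-24h by linear-up/log-down. Extrapolate with the terminal slope (lambda-z) from the last quantifiable sample to 24 hours whenever later samples are BLQ or were not collected, naming TB12 and TB13 on Day 3. State an acceptance rule for lambda-z and a fallback where it fails, such as an AUC over a window common to all products; in the simulation a linear AUC0-4h also recovered ratios of 0.714 and 0.858 without extra width. Report the percent extrapolated by product, and keep the linear calculation as a sensitivity analysis. Align Protocol 12.1.3, or record the difference in SAP section 9, which now declares the two documents aligned.

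The cost is a few lines of text and a setting in the software, with no new samples or visits. There are two small drawbacks. Lambda-z must be estimable from sparse late samples, and values will differ slightly from earlier studies that used the linear rule. The clean recovery in simulation is partly built in, because the simulated decline is exponential, the form that the extrapolation assumes.

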3.1 Primary Objective(s)

The main objective of this study is:

1. To describe the plasma concentration-time profile of nicotine and derived pharmacokinetic (PK) parameters of the single use of THS with either a regular or a menthol stick or of a single CIG.

Endpoints (Day 1 to Day 3)

Plasma nicotine concentration-time PK parameters (THS regular stick, THS menthol stick, and CIG separately):

- Maximum nicotine plasma concentration [C_{max}]
- Time to the maximum nicotine plasma concentration [T_{max}]
- Area under the curve of nicotine plasma concentration-time computed from T_0 to $T=24$ hours [AUC_{0-24h}]
- Area under the curve of nicotine plasma concentration-time computed from T_0 to the subject-specific time of maximum nicotine concentration [AUC_{0-t}]

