4.2 Rationale for Study Design

The single use of a THS with either a regular or menthol stick or of a single CIG will allow appropriate comparison between THS usage and CIG smoking, as well as comparison to published data [8-11].

Sampling time points for determination of nicotine concentrations were selected to ensure reliable estimation of PK parameters. Frequent sampling during the first 15 minutes from T_0 will be performed to reliably assess C_{max} , T_{max} , and AUC.

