## 2. OBJECTIVES AND ENDPOINTS

Objectives	Endpoints

Primary
 
To describe the plasma concentration-time profile of nicotine and derived pharmacokinetic (PK) parameters of a single use of THS with either a regular or a menthol stick or of a single combustible cigarette (CIG)
	
Plasma nicotine concentration-time PK parameters (THS regular stick, THS menthol stick, and CIG separately):
 
 
• Maximum nicotine plasma concentration [Cmax]
 
• Time to the maximum nicotine plasma concentration [Tmax]
 
• Area under the curve of nicotine plasma concentration-time computed from T0 to T=24 hours [AUC0-24h]
 
• Area under the curve of nicotine plasma concentration-time computed from T0 to the subject-specific time of maximum nicotine concentration [AUC0-Tmax]
 

Philip Morris Products S.A.  
 THS Induction device and regular or menthol sticks, P1-PK-12  
 [REDACTED]  
 CA39924

Secondary	
To evaluate pharmacodynamic (PD) effects (subjective effects) of a single use of a THS with either a regular or a menthol stick or of a single CIG.	
 
Score of CIG craving by the visual analogue scale (VAS) Craving assessment
 
Score of investigational product (IP) liking by the VAS Liking assessment
 
Score of intention to use the IP again by the VAS Intention to Use Again assessment
 

To evaluate the safety of test products during the study.	
 
Incidence of adverse events (AEs) and serious adverse events (SAEs)
 
Incidence of product events
 
Changes in electrocardiogram (ECG) from baseline (heart rate, PR, QRS, QT, QTcF interval)
 
Changes in vital signs from baseline (systolic and diastolic blood pressure, pulse rate and respiratory rate)
 
Concomitant medication
 
Changes in standard spirometry from baseline (FEV1, FEV1 % predicted, FVC, FVC % predicted, FEV1/FVC)
 
Changes from baseline in clinical chemistry, hematology, and urine analysis safety panel
 

[figure not shown]

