## 6.5 Statistical Analysis of Pharmacokinetic Parameters

### 6.5.1 Main Analysis

A mixed model analysis of variance (ANOVA) will be conducted on Cmax, AUC0-24h, and AUC0-Tmax endpoints in the natural logarithmic scale.

The model will include terms for sequence, period, product as fixed effects and subject as a categorical random effect modeling the within subject correlations.

The ANOVA analysis could be performed using the following SAS code:

```
PROC MIXED data=<> method=REML;
class subject sequence period product;
model log(parameter) = sequence period product/ddf=KR;
repeated product / subject=subject type=csh;
lsmeans product / pdiff=control("CIG") cl alpha=0.05;
RUN;
```

The results of this analysis for each of are presented in terms of geometric least square ratios and 95% confidence intervals for each THS / CIG ratio.

This approach is consistent with the guidelines in the European Medicines Agency's guidelines for bioequivalence investigations and FDA's Center for Drug Evaluation and Research.

The analysis of Tmax will be performed by conducting a Wilcoxon signed rank test and calculating the median Tmax for each product along with the Hodges-Lehmann estimate of the median difference between products, and the related 95% CI.

This analysis could be performed using the following SAS code:

```
PROC NPAR1WAY hl(refclass=<>) alpha=.05 data=<> hl;
class TRT;
var AVAL;
ods output HodgesLehmann=HodgesLehmann;
RUN;
```

Philip Morris Products S.A.  
 THS Induction device and regular or menthol sticks, P1-PK-12  
 [REDACTED] CA39924

---

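### The plan does not say whose Tmax ends AUC0-Tmax; on the natural reading the THS/CIG ratio mixes amount of exposure with time to peak

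*SAP*

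**What the plan says.** Protocol 3.1 lists four endpoints under the main objective. One is an area "computed from T_0 to the subject-specific time of maximum nicotine concentration", which the protocol labels AUC0-t. SAP 6.3 gives the same definition under the name AUC0-Tmax: "computed from T0 to the subject-specific time of maximum nicotine concentration [AUC0-Tmax". Neither sentence names the product whose Tmax is meant.

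Two other entries bear on the reading. SAP 2 lists "Plasma nicotine concentration-time PK parameters (THS regular stick, THS menthol stick, and CIG separately", so every parameter belongs to one product. SAP 6.3 defines Tmax as "Time to maximum nicotine plasma concentration Cmax", which is the time of that profile's own peak. No limit common to the products, and none tied to the cigarette, appears anywhere.

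The endpoint is then compared between products. SAP 6.5.1 states: "A mixed model analysis of variance (ANOVA) will be conducted on Cmax, AUC0-24h, and AUC0-Tmax endpoints in the natural logarithmic scale". Results are reported as geometric least-squares ratios with "95% confidence intervals for each THS / CIG ratio". Protocol 12.4.1 includes the geometric mean ratio for this area in the main estimand. Both documents (Protocol 12.4.1.6, SAP 6.5.3) say that no supplementary analysis is foreseen. Protocol 4.2 justifies the dense early schedule, "Frequent sampling during the first 15 minutes from T_0 will be performed", by the need to estimate Cmax, Tmax and AUC reliably.

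**The concern.** A crossover lets each subject's products be compared over the same minutes after T0. If the area for THS stops at the THS peak and the area for the cigarette stops at the cigarette peak, the ratio does not do this. A product that takes longer to peak is integrated for longer, so its area grows for a reason other than the amount of nicotine delivered.

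AUC0-Tmax is the only one of the three log-scale ratios that is an early area; AUC0-24h covers the whole day and Cmax is a single concentration. A reader who takes it as relative early exposure could see a value near or above 1 for a product that delivers less nicotine, more slowly, than the cigarette. No fixed-window early area is planned that would show the difference.

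**Working it through.** **Plan's own figure.** The documents give no expected value or precision for AUC0-Tmax. The only design figure, a precision of 0.191 or less in Protocol 12.7.3, concerns the Cmax ratios. It cannot be rebuilt, because the within-subject correlation it used is not stated, and it does not bear on this point.

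**Inputs from the documents.** Assumed geometric mean Cmax: menthol 10, regular 12, cigarette 14 ng/mL (Protocol 12.7.3.1). Half-life about 2 h (Protocol 12.1.2). Sampling at 4, 6, 8, 10, 12, 15 and 30 min, and linear trapezoids (SAP 6.1 and 6.3).

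**Assumed inputs.** Tmax of 6 or 8 min for the cigarette and 6 to 12 min for THS. Neither document gives a Tmax.

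**Step 1: linear rise to the peak.** Let r be the Cmax ratio and k the Tmax ratio, both THS/CIG.

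- Each area to its own Tmax is Cmax × Tmax / 2, so the own-Tmax ratio is r × k.
- For k ≥ 1, over the common window from 0 to the cigarette's Tmax, the ratio is r / k.

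Menthol, with 6 min for the cigarette and 8 min for THS:

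- Own Tmax: (10 × 8)/(14 × 6) = 80/84 = 0.95.
- Same first 6 min: THS has reached 10 × 6/8 = 7.5 ng/mL, so the ratio is 7.5/14 = 0.54.

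The own-Tmax ratio equals 1 when k = 1/r:

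- Menthol: 14/10 = 1.40.
- Regular: 14/12 = 1.17.

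**Step 2: direction.** Linear rise throughout.

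- Equal Tmax (k = 1): the ratio is r, that is 0.71 (menthol) or 0.86 (regular). No distortion.
- THS later, 8 against 12 min: 0.714 × 1.5 = 1.07 (menthol), 0.857 × 1.5 = 1.29 (regular).
- THS earlier, 8 against 6 min: 0.714 × 0.75 = 0.54 (menthol), below the Cmax ratio.
- Similar Cmax, as in study ZRHR-PK-02-JP (14.3 and 13.82 ng/mL, Protocol 12.7.3.1), 6 against 8 min: 1.035 × 1.333 = 1.38, further from 1.

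**Step 3: curves on the planned sampling times.** Constant-rate input up to Tmax, a terminal half-life of 2 h, and an assumed fast phase (half-life 15 min, weight 0.6), without measurement error:

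| Stick | Tmax CIG / THS (min) | Own Tmax | 0 to CIG Tmax | 0-15 min | 0-30 min |
|---|---|---|---|---|---|
| Menthol | 6 / 6 | 0.71 | 0.71 | 0.71 | 0.71 |
| Menthol | 6 / 8 | 0.96 | 0.55 | 0.68 | 0.71 |
| Menthol | 8 / 12 | 1.09 | 0.50 | 0.63 | 0.71 |
| Regular | 6 / 8 | 1.16 | 0.66 | 0.82 | 0.86 |
| Regular | 8 / 12 | 1.31 | 0.60 | 0.75 | 0.85 |

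The curved profiles agree closely with step 1. As THS slows, the own-Tmax ratio rises while the ratios over 0 to the cigarette's Tmax and over 0-15 min fall.

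**Step 4: precision.** Tmax is read from a discrete schedule, so its error enters the area as a multiplier. Simulated paired profiles (assumed log SD 0.6 between and 0.4 within subjects) gave these SDs of the within-subject log ratio:

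- 10% residual error, single 2 h decay (a nearly flat peak): 0.87-0.89 for own Tmax, against 0.57-0.62 for common windows.
- 5% residual error with the 15 min fast phase (a sharper peak): 0.68-0.70 against 0.57-0.61.

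The loss is therefore between 0.68/0.61 = 1.11 and 0.89/0.57 = 1.56 times, depending on the peak shape and error assumed.

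**The case against.** The strongest reply is that the text never says each product's own Tmax. A single limit per subject, such as that subject's cigarette Tmax, would also fit "to the subject-specific time of maximum nicotine concentration". This is right as far as it goes. Separate derivation by product and the Tmax definition make own-Tmax the natural reading, but it remains an inference. What stands either way is that the upper limit of an endpoint under the main objective is not pinned down.

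Second, the study is descriptive. It has no hypothesis, success criterion or significance level (Protocol 3.3 and 12.1.4). Cmax and Tmax are reported beside this ratio, Tmax differences are estimated, and concentrations are tabulated and plotted by product. A careful reader could see a later Tmax and discount the ratio. This stands and limits the consequence. It does not supply an early-exposure ratio over common minutes, which no planned analysis gives.

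Third, a limit at the cigarette's Tmax is not neutral: for a slower product it gives r / k, which falls below the Cmax ratio just as own-Tmax rises above it. This also stands. It favours one fixed window for everyone over a cigarette-anchored limit or a mixture of windows in one model.

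**Conclusion.** The point holds as a specification gap with a predictable effect. If each profile is integrated to its own Tmax, the AUC0-Tmax ratio is roughly the Cmax ratio times the Tmax ratio and should not be read as relative early exposure. The direction rests only on a near-linear rise to the peak. The size depends on Tmax values that the documents do not give; the break-even Tmax ratios of 1.40 and 1.17 need only the plan's own Cmax assumptions.

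Three stronger readings are tempting and unsupported. A reader might infer that the definition makes a slower product look closer to the cigarette. That is true only for lower THS Cmax with a modest delay: the ratio passes 1 with longer delays, moves away from 1 when Cmax is similar, and shifts the other way if THS peaks first. A reader might infer a fixed loss of precision, but the loss depends on how flat the peak is. A reader might also infer that the study's conclusions are unsafe. No decision rule rests on this ratio, and the Cmax, Tmax and AUC0-24h analyses are unaffected. The change is a worthwhile, inexpensive improvement.

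**What to change.** In SAP 6.3, state whose Tmax sets the upper limit of AUC0-Tmax. Add a partial AUC from 0 to 15 min, the same for all products and subjects, and include it in the model in SAP 6.5.1. Base the early-exposure THS/CIG ratio and its 95% confidence interval on this parameter. The samples needed (the pre-use sample and TB1 to TB6) are already scheduled, and the linear interpolation named in SAP 6.3 deals with a TB6 draw that is not exactly at 15 min.

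Keep AUC0-Tmax to each product's own Tmax as a descriptive parameter. If its ratio is retained because Protocol 12.4.1 names it in the estimand, report it beside Tmax with a note that the integration windows differ by product.

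The cost is one extra non-compartmental parameter, a row in the parameter and comparison tables, and an entry in SAP 9, which now declares full alignment with the protocol. The real downside is less emphasis on a parameter that the protocol names. Dropping its ratio altogether would depart from the stated estimand and is not needed.
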